8.4 DESIGN: Briefly describe the study design (e.g., observational, interventional, randomized, placebocontrolled, blinded, cross-over, cross-sectional, longitudinal, pharmacokinetic, etc.):

Design & Procedures

1. Subject recruitment: Participants will be recruited in [name] laboratory at UCSF. We plan to enroll a total of 240 subjects healthy volunteers (age range: 21-65 years) in order to complete 100 for the entire effort (R21 and R33 Phases combined). This corresponds to enrolling 68 subjects in the R21 (34/year) and 172 (58/year) during the R33 phase. This takes into account the expected rate of failure to: have a pupillary response to the fear conditioning paradigm (25%) and CO₂ challenge (50% - relevant for last 10 R21 and all R33 subjects); and to meet other screening criteria (see inclusion and exclusion criteria sections). These subjects will be recruited from the local community using posted flyers.

2. R21/R33 Components: R21 Phase:

First 30 Subjects, following the screening visit, these subjects will undergo 2-3 sessions separated by 1 week in which a promising electrode configuration (three promising configurations will each be tested in a cohort of 10 subjects) will be used with tDCS stimulation at increasing electrical dosage during which pupillometry will be carried out to determine the Anxiety Task (a test of responses to electrical pulses delivered to the fingers) or Auditory Oddball Test (AOT; a test of responses to rare vs common sounds) response. During pupillometry while undergoing tDCS, ECG, EEG, respiratory rate, or galvanic skin conductance measures may be obtained. A maximum of 5 total tDCS dosages and sham will be tested.

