R33 Phase: 60 subjects will participate in a double-blind, randomized, controlled, parallel-group trial. They will be randomized to either active or control treatment and at the first post-screening visit they will undergo electrical dose titration as described above for the treatment they are randomized to. For all titrations, during the 5 minutes between tDCS treatments an unblinded member of the study team not having contact with the subjects will compute their Anxiety Task or Auditory Oddball Test response (these tests will be used to determine optimal dosing in terms of the tDCS level that blocks the pupil response in these tests) and convey to the tDCS treatment physician whether to continue or stop titration. Subjects randomized to the control treatment will undergo a sham titration where the stop level will be randomly selected from the distribution of titration outcomes occurring in the R21 phase. Subjects will then return in 1 week and undergo optimal dose tDCS or control treatment for a single treatment session as described in the prior paragraph. Primary outcome will be the VAS-A "fearful" rating obtained at the end of tDCS/CO₂ inhalation. Anxiety Task or AOT pupil responses will be obtained every 10 minutes after the end of the tDCS/CO₂ inhalation period to map the duration of persistent effects on LC (heart rate and skin conductivity will also be obtained as exploratory measures). At the end of this session participation will end except that subjects will be called the next day to assess for adverse effects and care given if necessary. Data from the R21 phase will be used to provide justification for the larger R33 study, and prior to initiation of the R33 phase, the study will be submitted to the IRB for review/approval.

8.5 BACKGROUND AND SIGNIFICANCE: Briefly provide the background and significance of this study (e.g.

why is this study needed) (space limit: one half page):

If this is a first in humans study, please summarize the safety data from the animal studies. For pediatric drug or device studies, please identify if this is the first study in pediatric populations.

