2) Hypothesis 1b: In 10 controls in a cross-over study, 7.5% CO₂ inhalation significantly increases the VAS-A "fearful" rating compared to baseline rating. This will be tested with a RMANOVA where condition (7.5% CO₂ vs air) is the independent variable and VAS-A "fearful" rating is the repeated dependent measure.

3) Hypothesis 2a, 1b, 1a: In a cross-over study, active dose-personalized tDCS significantly suppresses the LC pupil response to 7.5% CO₂. This will be tested by carrying out a RMANOVA where treatment (active tDCS vs control) is the independent variable and mean resting pupil diameter is the repeated dependent measure. This will also establish that 7.5% CO₂ elicits an LC response as measured by mean pupil diameter (Hypothesis 1b) and whether subjects can guess whether they received active tDCS or the control to assess the viability of the control treatment (Hypothesis 1a).

4) Hypothesis 2b: Active tDCS will be safe in terms of there being no adverse effects of more than mild severity and rated to be possibly, probably, or definitely related to treatment.

R33 Testing R33 hypotheses assesses if the criteria for proceeding to further development are met.

1) Hypothesis 3a: Dose-personalized tDCS decreases VAS-A "fearful" rating compared to sham in a parallel-group, randomized, double-blind study. This will be determined by computing the effect size in terms of Cohen's D for the tDCS vs control treatment effect on the VAS-A "fearful" rating at the expected peak CO₂ effect (20 minutes after start of CO₂).

2) Hypothesis 3b: tDCS is safe as indicated by the absence of adverse effects of more than mild severity rated to be possibly, probably, or definitely related to treatment.

Secondary/Exploratory Analyses. Examples of Exploratory/Secondary analyses of interest include: 1) Testing if there are significant differences between active tDCS and the control therapy on the pupillary response to CO₂ in the R33 study; 2) Evaluating tDCS vs control treatment effect sizes for

other VAS-A items and the STAI in the R33 study; 3) mapping the time-course of effects on LC post-tDCS

8.26 REFERENCES: List only the 5-10 most relevant references (a separate bibliography can be attached for reference purposes if this study involves novel approaches, agents, or an emerging technology that the IRB may not be familiar with):

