decrease the "buzz" stimuli to the patient's level of comfort, as they self-report "annoying" but not "painful" level. The patient may stop at any time or have the stimulus reduced at any time. The number of stimulations delivered will be limited to 10 per 12 minute trial (stimulation associated with either the high or low tone). Parts of the task may become boring or repetitive. Efforts will be made to limit the number of trials administered per visit to minimize subject boredom and discomfort, while ensuring that adequate amounts of data are being collected.

Inhalation of 7.5% CO₂. The primary adverse effect of 7.5% CO₂ inhalation is the induction of Acute Fear which is also the reason that it is being carried out in this study. The fear is generally well-tolerated and resolves within roughly 10 minutes of the end of inhalation. A small percentage of subjects report increased sweating, tremor, tension, and tight muscles during or shortly after inhalation which is generally well tolerated. A gradual rise in blood pressure and pulse with a final systolic blood pressure rise of approximately 18 points, diastolic blood pressure rise of approximately 3 points, and heart rate elevation of approximately 8 points occurs with CO₂ gas as compared to when subjects received "air" inhalation. In rare circumstances severe anxiety could be elicited. There is no evidence that repeated inhalations increases the risks of severe anxiety in response to inhalation testing or in the year following the inhalations. Several studies have evaluated the effects of repeated inhalations with 7.5% CO₂ and higher percentages of CO₂ and not found evidence that there is an increase in fear elicited or an increase in adverse effects with repeated exposures (Poma et al., 2005; Verburg et al., 1998). In addition, a group of healthy non-anxious subjects undergoing repeated exposure to 20% CO₂ inhalation (N=155) were followed for up to a year and compared to a group of healthy non-anxious control subjects who breathed room air (N=56) and there was no evidence that the exposures to 20% CO₂ increased the risk for anxiety /panic during the year of follow-up (Prenoveau et al., 2006).

ECG. Skin irritation from the ECG electrode pads or pain when removing the pads is a possible risk.

12.3

MINIMIZING RISKS: Describe the steps you have taken to minimize the risks/discomforts to subjects. Examples include:

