The study structure is such that there will be 4 cohorts of subjects each consisting of 10 subjects. Each of the first 3 cohorts will be stimulated with a different tDCS electrode configuration to determine if we can find one which is tolerable and inhibits locus coeruleus activity (as indicated by inhibition of a pupil dilatory response). After each cohort we will carry out an interim analysis to determine if this was the case (80% had tolerability ratings of 2 or less and there was statistically significant inhibition of the pupillary response to the anxiety task or auditory oddball task). Each of these interim analyses will be reported to the DSMB. If after the 3 cohorts are completed and if none of the 3 tDCS configurations tested meet the success criteria, then the study will cease. If one of the tDCS configurations meets the success criteria then an additional 10 subjects will be run using the successful tDCS configuration and using 7.5% CO2 instead of the anxiety task or auditory oddball test to elicit a pupillary response.

13.3 * DATA AND SAFETY MONITORING BOARD (DSMB): Will a Data and Safety Monitoring Board (DSMB) be established: (REQUIRED)

Yes

No

13.4 DSMB DETAILS: Provide details from the DSMB's charter, including meeting frequency, and affiliations and qualifications of members: If the DSMB has not yet been established, submit these details to us as they become available.

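### Hypotheses 2b and 3b infer safety from a zero count with no confidence limit, denominator or arm comparison; if 30 R33 subjects are active, zero events still allows a true rate near 10%

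*Combined protocol and SAP*

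**What the plan says.** Section 8.25 has one safety hypothesis per phase. For R21, Hypothesis 2b reads "Active tDCS will be safe in terms of there being no adverse effects of more than mild severity", limited to effects rated possibly, probably or definitely related. For R33, Hypothesis 3b reads "tDCS is safe as indicated by the absence of adverse effects of more than mild severity", with the same relatedness condition. The R21 hypotheses serve as the Go-No-Go criteria, and the R33 hypotheses decide whether development continues. Neither safety hypothesis names an acceptable rate, a confidence limit, an analysis set or a comparator. The secondary analyses listed in 8.25 compare the arms on pupil response, other VAS-A items and the STAI, but not on adverse effects. The sample size justification in 10.3 does not address safety.

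Section 8.4 gives the R33 size and assignment: "60 subjects will participate in a double-blind, randomized, controlled, parallel-group trial" and "They will be randomized to either active or control treatment". No ratio is stated.

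Tolerability is handled separately. Subjects rate discomfort on a 0 to 4 Likert scale on which 3 is moderate (8.11), while adverse events are collected with the SAFTEE. The interim success criterion in 13.2 includes that "80% had tolerability ratings of 2 or less". The stopping rule in 13.2 closes a configuration once three subjects rate it 3 or higher, and any subject giving such a rating is withdrawn.

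**The concern.** Observing no events in a small group shows that the rate is probably not large. It does not show that the rate is negligible. With no limit attached, the reader cannot tell what the zero has ruled out, and the conclusion sounds the same for 10 subjects as for 1,000. Sections 12.3 and 13.2 both say that the risks of this form of stimulation are not well known, so earlier experience cannot fill the gap. The prior data cited in 9.4 concern serious effects and irreversible injury, which is a different threshold from more than mild.

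Two further omissions make the count hard to interpret. First, no denominator is named. Subjects with moderate or worse discomfort leave the study, and 60 is part of a target of 100 completers. If only completers are counted, and if discomfort and adverse effects tend to occur in the same people, selection helps to produce the zero. Second, stimulation is given during CO₂ inhalation, and 12.2 states that "A small percentage of subjects report increased sweating, tremor, tension, and tight muscles during or shortly after inhalation". Attribution then rests on a judgement for each event, with no use of the concurrent control. At stake is the safety half of the decision on further development.

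**Working it through.** The plan states no figure for safety precision, so there is none to reproduce. The check asks what a pass would show.

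**Inputs.** R33 total: 60 (8.4). Allocation ratio: not stated, so 1:1 (30 active, 30 control) is an assumption. R21: 10 cross-over subjects, 40 in all (8.4); Hypothesis 2b does not say which group it covers. Pass rule: zero related effects above mild (8.25).

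**Upper limit after zero events in n.** The exact binomial limit is 1 − 0.05^(1/n) one-sided 95%, and 1 − 0.025^(1/n) two-sided 95%. For n = 30: 1 − 0.05^(1/30) = 0.095 and 1 − 0.025^(1/30) = 0.116.

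| n | Possible reading | One-sided 95% | Two-sided 95% |
|---|---|---|---|
| 10 | R21 cross-over only | 25.9% | 30.8% |
| 20 | smaller R33 active arm | 13.9% | 16.8% |
| 30 | R33 active arm at 1:1 | 9.5% | 11.6% |
| 40 | all R21, or a 2:1 R33 active arm | 7.2% | 8.8% |
| 60 | both R33 arms pooled | 4.9% | 6.0% |

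The pooled row is included because 3b says only tDCS, and the study summary describes the control as a form of tDCS too.

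**Chance of passing at a true rate p.** This is (1 − p)^n. For n = 30:
- p = 1%: 0.99^30 = 0.74, so the rule fails 26% of the time even at this low rate.
- p = 2%: 0.98^30 = 0.55.
- p = 5%: 0.95^30 = 0.21.
- p = 10%: 0.90^30 = 0.042.

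These rates are illustrative; the documents give no expected or acceptable rate. A pass is weak evidence of a low rate, and a fail does not show a high one.

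**What an arm difference would add.** With 0/30 in both arms, the Wilson upper limit for each is 1.96²/(30 + 1.96²) = 3.84/33.84 = 0.113. The Newcombe 95% interval for the difference is then about ±11 percentage points. The difference is imprecise, so it can supplement the single-arm limit but cannot replace it.

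**The two scales.** Hypothesis 2a requires 8 of 10 subjects to be both tolerant (Likert) and suppressed (pupil response). Section 13.2 lets up to 20% of a cohort rate above 2, and its stopping rule acts only at the third such rating. Hypothesis 2b uses adverse-effect severity and relatedness. No passage says whether a Likert rating of 3 or 4 is an adverse effect above mild.

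**The case against.** The trial is exploratory, and the study summary seeks only preliminary evidence. Section 8.25 is a field for a brief summary. The DSMB, which includes a biostatistician, receives all adverse events and tolerability ratings and helps to make the Go decision, so 2b is not applied mechanically. Relatedness is rated in a double-blind design. All of this stands, and it bears on how serious the point is. None of it supplies a limit, a denominator or a planned comparison.

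Three stronger readings are tempting and should not be adopted.

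- A reader might infer that Hypothesis 2a accepts what 2b would reject. The documents do not show this. The two hypotheses use different scales, and the two failures that 2a permits may be failures of suppression. If 2b is stricter, it simply governs, since both are Go criteria. Nor is it valid to set the chance of at least one event in 40 subjects at a 5% rate (1 − 0.95^40 = 87%) against the 20% tolerability allowance. The 5% rate is not in the documents, 2b is not tied to 40 subjects, and the scales differ.
- A reader might infer that the control arm gives the background rate for all harms. It cannot do so for skin effects. The control is matched on skin current density, and 12.2 names skin irritation as a common tDCS effect, so an arm difference would tend to cancel it.
- A reader might infer that ordinary CO₂ symptoms will make tDCS fail. Section 12.2 describes them as generally well tolerated, and nothing shows that they would exceed mild or be rated related. It is possible, but not established.

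**Conclusion.** The concern holds in a limited form. Hypotheses 2b and 3b conclude safety from a zero count with no limit, denominator or arm comparison, and that conclusion is stronger than the data could support. Assuming 1:1 allocation, zero events in 30 active subjects is compatible with a true rate of up to 9.5% (one-sided) or 11.6% (two-sided). No plausible R33 denominator brings the one-sided limit below 4.9%. The calculation takes subjects as independent and counts each subject once. The relation between Likert discomfort and adverse-effect severity is an unstated definition that needs reconciling, not a demonstrated contradiction. Nothing here suggests that tDCS is unsafe.

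**What to change.** In section 8.25:

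1. Report the number and rate of subjects with related adverse effects above mild in each arm, with exact 95% limits.
2. Define the safety set as all subjects exposed to stimulation, including those withdrawn at titration for discomfort.
3. Add the active-control risk difference with its interval as a supplement. State that it helps to separate CO₂ symptoms and LC-specific effects, but not skin effects shared with the matched control, so it is read beside the single-arm rates.
4. Word the R33 conclusion as no events in n exposed, with the true rate below the stated upper limit, instead of safe. State the R33 allocation ratio so that n is known in advance.
5. State whether a discomfort rating of 3 or more counts as an adverse effect above mild under 2b, and which R21 subjects 2b covers, so that 8.25 and 13.2 are reconciled.

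The cost is SAP wording and one small table, with no added subjects and no design change. The downside is a more modest safety claim.

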Note: This question is frequently answered incorrectly. If any drugs or biologics, approved or unapproved, are being administered under this protocol, you should check 'Yes' unless you are *absolutely* sure that **NONE of the drugs are part of the research protocol. Tip: Ask the PI or the sponsor if you are not sure how to answer this question.**

9.3 * MEDICAL DEVICES: Are you **STUDYING any medical devices, in vitro diagnostics, or assays that are either approved or unapproved: (REQUIRED)**

Yes No

9.4 * NSR: Are you requesting a Non-Significant Risk (NSR) determination for an investigational device:

(REQUIRED) Note: an NSR determination is different from an Investigational Device Exemption

(IDE). Check the Help link for more guidance on what types of devices can qualify for an NSR determination.

Yes No

* Explain why the use of the device in this study poses a non-significant risk: (REQUIRED)

Transcranial Direct Current Stimulation (tDCS) TDCS involves non-invasive transcranial electrical stimulation using direct current with a sustained intensity of a few milliamperes and duration of up to tens of minutes. Administered in this way tDCS is a safe procedure (See Bickson et al., 2016 attached). Evidence from relevant animal models indicates that brain injury by such Direct Current Stimulation occurs at predicted brain current densities (6.3–13 A/m) that are over an order of magnitude above those produced by tDCS such as we will administer it (Bickson et al., 2016). To date, the use of conventional tDCS protocols in human trials (≤ 40 min, ≤ 4 milliamperes, ≤ 7.2 Coulombs) has not produced any reports of a Serious Adverse Effect or irreversible injury across over 33,200 sessions and 1000 subjects with repeated sessions and including a wide variety of subjects, including persons from potentially vulnerable populations (Bickson et al., 2016). The US Food and Drug Administration (FDA) considers trials of tDCS as nonsignificant risk, which means tDCS is without reasonable expectation of any Serious Adverse Effect (as defined here) (Bickson et al., 2016). As of the publishing of the Bickson et al., article, the FDA "MedWatch" database search returns no reports for "tDCS" or "transcranial Direct Current Stimulation."

Attach any documentation you have from the manufacturer and/or FDA to support this determination.

9.5 LIST THE DEVICES: List the medical devices or in vitro diagnostics to be studied or used. In the device details screen you will be asked questions such as:

- Whether the device is FDA approved or investigational
- Medicare device category
- If the device will be provided at no cost
- If an IDE is necessary, the IDE number, and who holds the IDE
- Risk category of the device
- FDA status of the device

Please see the [UCSF IRB website](#) for more details about the use of devices in research, including the [Investigator Checklist for Significant Risk, Non-Significant Risk, and/or IDE Exempt Device Studies](#) [Verification of IDE numbers: If the sponsor's protocol does not list the IDE number, you](#)

must submit documentation from the sponsor or FDA identifying the IDE number for this study. Attach this documentation in the Other Study Documents section of the Initial Review Submission Packet. If you have any correspondence from the FDA or sponsor regarding this device, please attach it to the application.

NeuroConn DC Stimulator MC-
No Yes 4

Manufacturer/Supplier of Device Rogue Resolutions

Medicare Category A B

Where will the Devices Be Stored Langley Porter Psychiatric Institute

Will Devices be supplied at no Cost Yes

Is this a HDE (HDE) No

HDE Number

Is the Device FDA Approved No

Is this a new device or a new use
of an already approved device Yes

Is an IDE necessary No

IDE Number

Who holds the IDE N/A

IDE Details

In the opinion of the sponsor,
select the level of risk associated
with this device No Significant Risk

9.6 * Is this an expanded access or compassionate use protocol, meaning the primary purpose is to diagnose, monitor or treat a patient's condition, rather than the collection of safety and efficacy data of the experimental agent: (REQUIRED)

Yes No

10.1 ENROLLMENT TARGET: How many people will you enroll:

If there are multiple participant groups, indicate how many people will be in each group:

Participants will be recruited in [name] laboratory at UCSF. We plan to enroll a total of 240 subjects healthy volunteers (age range: 21-65 years) in order to complete 100 for the entire effort (R21 and R33 Phases combined). This corresponds to enrolling 68 subjects in the R21 (34/year) and 172 (58/year) during the R33 phase. This takes into account the expected rate of failure to: have a pupillary response to the Auditory Oddball Test (25%) and CO₂ challenge

(50% - relevant for last 10 R21 and all R33 subjects); and to meet other screening criteria (see inclusion and exclusion criteria sections). These subjects will be recruited from the local community using posted flyers.

10.3 SAMPLE SIZE JUSTIFICATION: Explain how and why the number of people was chosen. For multi-site studies, this is referring to the number that will be enrolled across all sites:

Given the nature of the R21/R33, we have few analyses for which consideration of power is relevant. These include the determination of whether there is a statistically significant difference in pupil response to the Anxiety Task or the rare and common stimuli in Auditory Oddball Task (AOT) and determination of whether in the R21 cross-over study active tDCS has a significantly greater effect on the pupil response to CO₂ than sham. For the Auditory Oddball Task (AOT), in our pilot work where we were able to demonstrate differences between rare and common stimuli and the suppressing effects of tDCS (See Preliminary Studies). N=10 subjects in our R21 pilot cross-over study will be sufficient based on our pilot work (C.3.5). We estimate that the size of the effect of a dose-personalized, electrode configuration optimized tDCS vs control therapy will be at least as large as the effect size we observed in our preliminary work with a pilot electrode configuration where we found that in 4/5 subjects we could demonstrate a statistically significant suppression of the AOT pupil response compared with no stimulation which serves as a pilot proxy for the control therapy.

10.4 * PARTICIPANT AGE RANGE: Eligible age ranges: (REQUIRED)

- 0-6 years
- 7-12 years
- 13-17 years
- 18-64 years
- 65+

10.5 * STUDY POPULATIONS: Data will be collected from or about the following types of people (check all that apply): (REQUIRED)

- Inpatients
- Outpatients
- Family members or caregivers
- Providers
- People who have a condition but who are not being seen as patients
- Healthy volunteers
- Students
- Staff of UCSF or affiliated institutions
- None of the above

10.6 * SPECIAL SUBJECT GROUPS: Check the populations that may be enrolled: (REQUIRED)

- Children / Minors
- Subjects unable to consent for themselves
- Subjects unable to consent for themselves (emergency setting)
- Subjects with diminished capacity to consent
- Subjects unable to read, speak or understand English
- Pregnant women
- Fetuses
- Neonates
- Prisoners
- Economically or educationally disadvantaged persons
- None of the above

10.7 INCLUSION CRITERIA: Briefly describe the population(s) that will be involved in this study. Include anyone that data will be collected from or about (e.g. patients, healthy controls, caregivers, providers, administrators, students, parents, family members, etc.):

Inclusion/Exclusion criteria were chosen to allow us to meet study aims and are comparable to those used in [name] prior study of transcranial alternating current (tACS) vestibular stimulation of healthy controls. Inclusion Criteria. 1) Age between 21-65; 2) Use of effective method of birth control for women of childbearing capacity; 3) Willing and able to provide informed consent; 4) Have a significant difference between the mean pupil diameter in response to rare vs common tones in the Auditory Oddball Test (AOT) or the Anxiety Task; 5) The 10 subjects in the R21 cross-over study and all of the R33 subjects must have a 26% increase in VAS-A "fearful" response to 7.5% CO₂ at the first CO₂ challenge session; 6) Able to follow study procedures.

10.8 EXCLUSION CRITERIA: List any exclusion criteria (e.g. reasons why someone would not be included in the study):

Exclusion Criteria. 1) Current or past Axis I DSM-IV disorder based on the MINI; 2) Current or past history of substance abuse or dependence (excluding nicotine) based on history or positive urine toxicology; 3) Current unstable medical condition; 4) Any current neurological condition or medical condition that is known to affect pupillary function, mood/anxiety, or neurologic function generally; 5) Pregnancy based on Urine Pregnancy Test; 6) Women who are breast feeding; 7) Use of medications known to affect CNS function within 5 half-lives screening; 8) Use of magnet controlled or programmed devices such as pacemakers, programmable ventriculoperitoneal shunts, or vagal nerve stimulators.

10.9 * RESEARCH CONDUCTED ON PATIENT CARE WARDS: Do any study activities take place on patient care units at UCSF medical facilities: (REQUIRED)

Yes No

